11.3 Vital Signs

Descriptive statistics for vital signs (oral temperature, respiratory rate, systolic and diastolic blood pressure, pulse rate, and body weight) and changes from baseline values at each visit and at EOT will be presented by treatment group.

Vital sign values will be considered PCS if they meet both the observed-value criteria and the change from baseline criteria listed in [Table 11.3-1](#). The number and percentage of participants with PCS postbaseline values will be tabulated by treatment group for the double-blind Treatment Period. The percentages will be calculated relative to the number of participants with available non-PCS baseline (for respiratory rate & temperature) or baseline values (for other parameters) and at least 1 postbaseline assessment for the double-blind Treatment Period. The numerator will be the total number of participants with available baseline values and at least 1 PCS postbaseline value for the double-blind Treatment Period. A supportive tabular display of participants with PCS postbaseline values will be provided, including the PID number, trial center number, and baseline and all postbaseline (including non-PCS) values.

In addition, a tabular display showing all AEs that occurred in participants who had PCS postbaseline vital signs values will be provided.

Table 11.3–1. Criteria for Potentially Clinically Significant Vital Signs

Parameter	Flag	Criteria ^a	
		Observed Value	Change From Baseline
Sitting systolic blood pressure, mm Hg	High	≥ 180	Increase of ≥ 20
	Low	≤ 90	Decrease of ≥ 20
Sitting diastolic blood pressure, mm Hg	High	≥ 105	Increase of ≥ 15
	Low	≤ 50	Decrease of ≥ 15
Sitting pulse rate, bpm	High	≥ 120	Increase of ≥ 15
	Low	≤ 50	Decrease of ≥ 15
Weight, kg	High	—	Increase of ≥ 7%
	Low	—	Decrease of ≥ 7%
Respiratory Rate, bpm	High	≥ 24	—
	Low	≤ 8	—
Temperature, °C	High	≥ 38	—
	Low	≤ 35	—

a A postbaseline value is considered potentially clinically significant if it meets both the observed-value and the change from baseline criteria.

bpm = beats per minute.

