2.2 List of Figures

Figure 4.1–1. RLM-MD-01 / RLM-MD-02 Study Schematic 8

3.0

List of Abbreviations

aCSR	abbreviated clinical study report
AE	adverse event
AESI	adverse event of special interest
ALT	alanine aminotransferase
ALP	alkaline phosphatase
ANCOVA	analysis of covariance
ANOVA	analysis of variance
AST	aspartate aminotransferase
CFB	change from baseline
CI	confidence interval
CMH	Cochran-Mantel-Haenszel
DG	diabetic gastroparesis
DGSSD	Diabetic Gastroparesis Symptom Severity Diary
DGSSS	Diabetic Gastroparesis Symptom Severity Score
DGSSS-SR	DGSSS Study Responder
GEBT	gastric emptying breath test
eCRF	electronic case report form
ECG	electrocardiogram, electrocardiographic
eDiary	electronic diary
EOT	end of trial
ITT	intent to treat
IP	investigational product

LSMs	Least squares means
MAR	missing at random
MCMC	Monte-Carlo Markov chain
MI	multiple imputation
mITT	modified intent to treat
MMRM	mixed-effects model with repeated measures
MNAR	missing not at random
OC	observed cases
OR	odds ratio

PCS	potentially clinically significant
QTc	QT interval corrected for heart rate

QTcB	QT interval corrected for heart rate using the Bazett formula (QTcB = QT/(RR) ^{1/2})
QTcF	QT interval corrected for heart rate using the Fridericia formula (QTcF = QT/(RR) ^{1/3})
RM	rescue medication
RLM	Relamorelin
SAE	serious adverse event
SAP	statistical analysis plan
SE	standard error
SI	Le Système International d'Unités (International System of Units)
SOC	system organ class
TBL	total bilirubin
TEAE	treatment-emergent adverse event
TESAE	treatment-emergent serious adverse event
TFLs	Tables/Figures/Listings
V-SR	vomiting study responder

4.0 **Introduction**

This statistical analysis plan (SAP) provides a more technical and detailed elaboration of the statistical analyses of the efficacy and safety data that will be performed for Study RLM-MD-01 and separately for study RLM-MD-02 as outlined and/or specified in their respective protocols:

- RLM-MD-01: Final protocol (version dated 13 Jul 2017) and the most recent amendment (Amendment 4 dated 08 Feb 2019).
- RLM-MD-02: Final protocol (version dated 3 Oct 2017) and the most recent amendment (Amendment 3 dated 05 March 2019).

Specifications of tables, figures, and data listings for each study are contained in a separate document. [REDACTED]

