The study was early/prematurely terminated on 04 September 2020 when the letter explaining termination activities was sent to all investigators. As a result, the original planned full analyses for the study are no longer applicable for the terminated study. Only abbreviated clinical study report (aCSR) for RLM-MD-01 and RLM-MD-02 will be developed.

The statistical analysis plan (SAP) amendment 2 is based on the amendment #1 SAP dated 29 Sep 2020. The major change to the amendment #1 SAP is to add descriptive analyses for the primary and secondary efficacy endpoints for the results posting on ClinicalTrials.gov and EudraCT (European Union Drug Regulating Authorities Clinical Trials Database) and add the COVID-19 data listing. Please refer to Section [19.2](#) Appendix 2 for details of the outlined analyses for the aCSR.

4.1 **Study Design**

Studies RLM-MD-01 and RLM-MD-02 are identical, designed as global, multicenter, randomized, double-blind, placebo-controlled, parallel-group in participants with diabetic gastroparesis.

In each study, approximately 600 eligible participants will be randomly assigned in a ratio of 1:1 to 1 of 2 treatment groups as follows:

[figure not shown]
- Treatment Group 1: Relamorelin (RLM) 10 µg BID (n=300)
- Treatment Group 2: Placebo BID (n=300)

The duration of each study is 18 weeks, including a 4-week Screening Period, a 2-week single blind Run-in Period, and a 12-week Treatment Period:

[figure not shown]
- Run-in Period: Participants who meet initial study entry criteria during the Screening Period will enter a 2-week Run-in Period, during which they will self-administer single-blind placebo twice daily subcutaneously. Using an electronic hand-held device, participants will report their daily symptoms via the Diabetic Gastroparesis Symptom Severity Diary (DGSSD) as well as their overall global impression of status, treatment satisfaction, treatment compliance, and use of rescue medication.
- 12-week Treatment Period: Participants who meet study entry criteria at the end of the Run-in Period, will be randomized 1:1 to blinded treatment with relamorelin 10 µg or placebo, and will continue to use the electronic hand-held device for reporting of their symptoms via the DGSSD as well as their overall global impression of status and change, treatment satisfaction, compliance, and use of rescue medication.

[figure not shown]

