11.2 Clinical Laboratory Parameters

Descriptive statistics for clinical laboratory values (in SI units) and changes from the baseline values at each assessment time point will be presented by treatment group for the following laboratory parameters:

Hematology	Platelet count	RBC count	Hemoglobin	Hematocrit
	% Reticulocytes	WBC count	Neutrophils	Lymphocytes
	Monocytes	Eosinophils	Basophils	
Clinical Chemistry	BUN	Creatinine	Fasting blood glucose	Hemoglobin A1c
	Potassium	Chloride	Bicarbonate	Sodium
	Calcium	Phosphorus	Uric acid	Aspartate
	aminotransferase	Alanine aminotransferase		Alkaline
	phosphatase	Total bilirubin	Direct bilirubin	Total protein
	Albumin	cholesterol	triglycerides	HDL
	cholesterol	LDL cholesterol		
Other Laboratory Assessments	C-peptide			
Urinalysis	pH	Specific gravity		

Clinical laboratory test values will be considered potentially clinically significant (PCS) if they meet either the lower-limit or higher-limit PCS criteria listed in [Table 11.2-1](#). The number and percentage of participants who have PCS postbaseline clinical laboratory values will be tabulated by treatment group for the double-blind Treatment Period. The percentages will be calculated relative to the number of participants with available non-PCS baseline values and at least 1 postbaseline assessment for the double-blind treatment period. The numerator will be the total number of participants with available non-PCS baseline values and at least 1 PCS postbaseline value for the double-blind Treatment Period. A supportive tabular display of participants with PCS postbaseline values will be provided, including the PID number, trial center number, and baseline and all postbaseline (including non-PCS) values.

In addition, tabular displays showing all AEs that occurred in participants who had PCS postbaseline clinical laboratory values will be provided.

Shift tables from baseline to end of trial (EOT) for clinical laboratory parameters will be presented by treatment group for the following categories: low, normal, and high.

Table 11.2-1. Criteria for Potentially Clinically Significant Laboratory Tests

Parameter	SI Unit	Lower Limit	Higher Limit
CHEMISTRY			
Albumin	g/L	< 0.9 * LLN	> 1.1 * ULN
Alanine Aminotransferase (ALT)	U/L	—	≥ 3 * ULN
Alkaline Phosphatase	U/L	—	≥ 3 * ULN
Aspartate Aminotransferase (AST)	U/L	—	≥ 3 * ULN
Calcium	mmol/L	< 0.9 * LLN	> 1.1 * ULN
Chloride	mmol/L	< 0.9 * LLN	> 1.1 * ULN
Cholesterol	mmol/L	—	> 1.6 * ULN
Creatinine	µmol/L	—	> 1.3 * ULN

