11.4 Electrocardiogram

Descriptive statistics for ECG parameters (heart rate, RR interval, PR interval, QRS interval, QT interval, and QTc) and changes from baseline values at each assessment time point to the end of study will be presented by treatment group. The QTc will be calculated using both the Bazett and Fridericia corrections.

Electrocardiographic parameter values are considered PCS if they meet or exceed the higher-limit PCS criteria listed in [Table 11.4–1](#). The number and percentage of participants with PCS postbaseline ECG values will be tabulated by treatment group for the double-blind treatment period. The percentages will be calculated relative to the number of participants with available non-PCS baseline values and at least 1 postbaseline assessment for the double-blind treatment period. The numerator is the total number of participants with available non-PCS baseline values and at least 1 PCS postbaseline value for the double-blind treatment period. A supportive tabular display of participants with PCS postbaseline values will be provided, including the PID number, baseline, all postbaseline (including non-PCS) values, and change from baseline.

In addition, a tabular display showing all AEs that occurred in participants who had postbaseline PCS ECG values will be provided.

Table 11.4-1. Criteria for Potentially Clinically Significant Electrocardiographic Values

Parameter	Unit	Criterion Value ^a	Change from Baseline ^a
QRS duration	msec	≥ 150	—
PR interval	msec	≥ 250	—
QTc (QTcB, QTcF) interval	msec	> 500	Increase of > 60

^a post-baseline (end-of-study or post-dose) value will be considered potentially clinically significant if it meets the criterion value or the change from baseline or pre-dose value.

PCS = potentially clinically significant; QTc = corrected QT interval; QTcB = QT interval/**RR**^{1/2}; QTcF = QT interval/**RR**^{1/3}.

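### SAP 11.3: for respiratory rate and temperature, the PCS numerator can count participants whom the PCS denominator excludes

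*SAP*

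**What the plan says.** SAP 11.3 sets the denominator in two parts. It opens "The percentages will be calculated relative to the number of participants with available non-PCS baseline (for respiratory rate" (the parenthesis goes on to name temperature) and continues "or baseline values (for other parameters) and at least 1 postbaseline assessment for the double-blind Treatment Period". So respiratory rate and temperature need a baseline that is not itself PCS, while blood pressure, pulse and weight need only a baseline.

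The next sentence gives a single numerator for every vital sign: "The numerator will be the total number of participants with available baseline values and at least 1 PCS postbaseline value".

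The footnote to Table 11.3-1 defines the flag: "A postbaseline value is considered potentially clinically significant if it meets both the observed-value and the change from baseline criteria". For respiratory rate (24 or more, 8 or less) and temperature (38 °C or more, 35 °C or less), the change column holds a dash.

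The neighbouring sections treat the same kind of table differently. For laboratory values, SAP 11.2 says "The numerator will be the total number of participants with available non-PCS baseline values and at least 1 PCS postbaseline value". For ECG values, SAP 11.4 says "The numerator is the total number of participants with available non-PCS baseline values and at least 1 PCS postbaseline value". In both sections the denominator carries the same non-PCS condition.

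**The concern.** A percentage of participants should have a numerator drawn from its denominator. In SAP 11.3 the baseline condition is split by parameter in the denominator, but the split is not carried into the numerator. For respiratory rate and temperature the two sets therefore differ.

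The affected participants are those already abnormal before double-blind dosing and abnormal again afterwards. Excluding them from the denominator points to a rate of newly arising abnormality. Leaving them in the numerator adds abnormality that was already present. The error can only raise the reported percentage. It would also distort the comparison between arms to the extent that the number of such participants differs between them.

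**Working it through.** The documents report no figure that depends on this rule, so there is nothing to reproduce. The check compares the sets and then does the arithmetic for each affected participant.

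**Step 1. Can a baseline value be PCS?** A dash is read here as no criterion of that type. SAP 11.3 supports this reading, because its denominator presupposes that a respiratory-rate or temperature baseline can be PCS.
- Blood pressure and pulse need an observed value and a change; weight needs a change only. A baseline has no change from itself, so it cannot be PCS. Requiring just an available baseline is correct for these.
- Respiratory rate and temperature need the observed value only, so a baseline can be PCS.

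**Step 2. Baseline condition, section by section.**

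| Section and parameter | Denominator | Numerator | Match? |
|---|---|---|---|
| 11.2 Laboratory | non-PCS | non-PCS | yes |
| 11.4 ECG | non-PCS | non-PCS | yes |
| 11.3 Blood pressure, pulse, weight | any available | any available | yes |
| 11.3 Respiratory rate, temperature | non-PCS | any available | **no** |

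The numerator sentence does not repeat the requirement for a later assessment. That is harmless, because a PCS postbaseline value implies one. SAP 16.4 uses all postbaseline assessments to decide PCS status, so one later abnormal value is enough to place a participant in the numerator.

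**Step 3. Formula.** For one arm, let N be the number with a baseline and a later assessment, b the number PCS at baseline, k the number of those who are PCS again (k ≤ b), and x the number of new cases among the rest.
- As written: (x + k)/(N − b)
- With matched sets: x/(N − b)
- Excess: k/(N − b), which is k/(N − k) when b = k

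**Step 4. Numbers.** SAP 4.1 plans that "approximately 600 eligible participants will be randomly assigned in a ratio of 1:1 to 1 of 2 treatment groups", which gives N = 300 per arm. The values of k are illustrative and are not estimates.

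| k (with b = k) | Excess at N = 300 |
|---|---|
| 0 | 0/300 = 0 |
| 1 | 1/299 = 0.33 percentage points |
| 2 | 2/298 = 0.67 percentage points |
| 3 | 3/297 = 1.01 percentage points |

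Example: with x = 3 and k = 1, the table would show (3 + 1)/299 = 1.34% as written and 3/299 = 1.00% with matched sets. In a smaller arm each such participant weighs more: at an assumed N = 150, k = 1 adds 1/149 = 0.67 percentage points.

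**The case against.** The strongest reply is that this is a drafting slip with an obvious intent. The restriction is stated in the sentence just before, the laboratory and ECG sections use matched sets, and a programmer might well apply the condition to both counts. That is plausible, and it is why the point is minor. But the SAP does not say so, and two programmers following the text could produce different tables.

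Second, the rule may affect no output. SAP 4.0 says that, after early termination, the full analyses as planned no longer apply and only an abbreviated report will be written. It refers to an appendix for the contents, which is not in the text available here. It also says "Specifications of tables, figures, and data listings for each study are contained in a separate document"; that document was not available either. So it cannot be checked whether this table is produced, or whether its specification already uses matched sets. This stands, and it makes the consequence conditional. It does not make the sentence correct.

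Third, the supportive display in SAP 11.3 lists baseline and all later values for participants with a PCS postbaseline value. Anyone affected can be found there, which is real mitigation.

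Two stronger readings are tempting, and the documents support neither:
- A reader might infer a large distortion, since the ratio as written could exceed 100% if enough participants were PCS at both times. No passage gives a rate of abnormal respiratory rate or temperature at baseline or later, so a large effect would rest on invented counts.
- A reader comparing the neighbouring PCS tables might infer that the potassium upper limit in Table 11.2-1 (above 2.0 × ULN, where sodium, chloride and calcium have 1.1 × ULN) is also an error. That table sets limits analyte by analyte (for example creatinine 1.3, cholesterol 1.6 and fasting glucose 2.5 × ULN), and nothing in the documents contradicts the potassium entry.

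**Conclusion.** The point holds as a minor internal inconsistency. Followed literally, SAP 11.3 gives a ratio for respiratory rate and temperature that is not a proportion whenever someone is PCS both at baseline and later. The bias is upward: 0.33 percentage points for one such participant in an arm of 300, and nil if there is none. This assumes the planned arm size, complete baseline and follow-up assessment, and nobody else PCS at baseline. The true number of such participants is unknown.

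The mismatch itself is certain from the text; its practical effect is not. It concerns two descriptive safety parameters and touches no hypothesis test, alpha level or sample size. The documents do not show that any reported result is wrong.

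**What to change.** In SAP 11.3, let the numerator repeat the denominator's split. For respiratory rate and temperature, count participants with a non-PCS baseline and at least one PCS value afterwards. For the other vital signs, keep the present condition of an available baseline. This gives respiratory rate and temperature the matched sets already used in SAP 11.2 and 11.4.

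Apply it in any report that produces this table, and check that the separate table specification agrees. The same SAP governs RLM-MD-01, so one edit serves both studies. The cost is one qualifier in one sentence; no new data and no change to any other analysis are needed.

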11.4 Electrocardiogram

Descriptive statistics for ECG parameters (heart rate, RR interval, PR interval, QRS interval, QT interval, and QTc) and changes from baseline values at each assessment time point to the end of study will be presented by treatment group. The QTc will be calculated using both the Bazett and Fridericia corrections.

Electrocardiographic parameter values are considered PCS if they meet or exceed the higher-limit PCS criteria listed in [Table 11.4–1](#). The number and percentage of participants with PCS postbaseline ECG values will be tabulated by treatment group for the double-blind treatment period. The percentages will be calculated relative to the number of participants with available non-PCS baseline values and at least 1 postbaseline assessment for the double-blind treatment period. The numerator is the total number of participants with available non-PCS baseline values and at least 1 PCS postbaseline value for the double-blind treatment period. A supportive tabular display of participants with PCS postbaseline values will be provided, including the PID number, baseline, all postbaseline (including non-PCS) values, and change from baseline.

In addition, a tabular display showing all AEs that occurred in participants who had postbaseline PCS ECG values will be provided.

Table 11.4-1. Criteria for Potentially Clinically Significant Electrocardiographic Values

Parameter	Unit	Criterion Value ^a	Change from Baseline ^a
QRS duration	msec	≥ 150	—
PR interval	msec	≥ 250	—
QTc (QTcB, QTcF) interval	msec	> 500	Increase of > 60

^a post-baseline (end-of-study or post-dose) value will be considered potentially clinically significant if it meets the criterion value or the change from baseline or pre-dose value.

PCS = potentially clinically significant; QTc = corrected QT interval; QTcB = QT interval/**RR**^{1/2}; QTcF = QT interval/**RR**^{1/3}.

11.5 Study Specific Assessments

Study-specific assessments (HbA1c, IGF-1 etc.) are summarized as part of the overall clinical laboratory assessments.

11.6 Other Safety Parameters

11.6.1 Physical Examination

Any new physical examination abnormality identified on the postbaseline physical examination or any physical examination abnormality noted as worsened from Screening (Visit 1) to the postbaseline physical examination will be reported as an AE if considered by the investigator to be clinically significant. No separate data analysis for physical exams is planned.

11.6.2 Potential Hy's Law

Potential Hy's Law criteria within a 24 hour window is defined by a post baseline elevation of alanine aminotransferase (ALT) or aspartate aminotransferase (AST) $\geq 3x$ ULN, along with total bilirubin (TBL) $\geq 2x$ ULN and a non-elevated alkaline phosphatase (ALP) $< 2x$ ULN, all based on blood draws collected within a 24 hour period.

Potential Hy's Law criteria without time window (e-DISH) is defined by maximum of post baseline elevation of ALT or AST $\geq 3x$ ULN, along with maximum of post baseline elevation of TBL $\geq 2x$ ULN and a non-elevated alkaline phosphatase (ALP) $< 2x$ ULN.

Participants who meet the potential Hy's Law criteria from the first dose of study drug to within 30 days after the last dose of study treatment will be summarized. Supportive tabular displays will also be provided.

11.7 Subgroup Analyses

Selected TEAE summaries (TEAEs by SOC/PT and treatment related TEAEs by SOC/PT) will be presented by selected subgroups as below:

- Diabetes type (Type I / Type II)
- Baseline HbA1c (<9% vs >=9%)
- Gender

13.0 **Interim Analysis**

[figure not shown]
No interim analysis is planned for this study.

14.0 Determination of Sample Size

The sample size and statistical power for the DGSSS endpoint was assessed by simulation. Data were simulated for the DGSS over time under the assumption of a multivariate normal distribution and based on mean responses in Study RM-131-009 variance -covariance structure ([Table 14-1](#)). A missing completely at random (MCAR) dropout rate of 20% by Week 12 was assumed for each treatment.

Vomiting response rates were assumed to be those observed in Study RM-131-009 (26% and 11% for treatment and placebo respectively). Sample size was assessed using the POWER procedure in SAS.

The sample size of approximately 300 participants per arm will provide more than 90% power to reject at least one of the primary null hypotheses using the multiplicity approach described in [Section 10.3](#).

15.0 Statistical Software

Statistical analyses will be performed using [REDACTED] SAS on a Linux operating system.

